#### 16.311 Interim Analysis: Enter 15 evaluable patients into the study. If 10 or fewer successes are observed in the first 15 evaluable patients, we will consider this regimen ineffective in this patient population and terminate the study. Otherwise, if the number of successes is at least 11, we will continue accrual.

16.312 Final Decision Rule: Enter an additional 19 evaluable patients into the study. If 25 or fewer successes are observed in the first 34 evaluable patients, we will consider this regimen ineffective in this patient population and terminate this study. Otherwise, if the number of successes is at least 26, this will be considered evidence of promising activity and the treatment may be recommended for further testing in subsequent studies in this population.

16.313 Over Accrual: If more than the target number of patients are accrued, the additional patients will not be used to evaluate the stopping rule or used in any decision making process.

16.314 NOTE: We will not suspend accrual at the interim analysis to allow the first 15 patients to become evaluable, unless undue toxicity is observed. Given the limited overall sample size and the inclusion of an adverse events stopping rule, we feel it is ethical to not halt accrual for the interim analysis. However, if accrual is extremely rapid, we may temporarily suspend accrual in order to obtain safety data on these patients before re-opening accrual to further patients.

16.32 Power and Significance Level: Assuming that the number of successes is binomially distributed, the significance level is .09, i.e. there is a 9% chance of finding the drug to be effective when it truly is not. The probability of declaring that this regimen warrants further study (i.e. statistical power) and the probability of stopping at the interim analysis under various success proportions can be tabulated as a function of the true success proportion as shown in the following table.

If the true success proportion is...	0.65	0.70	0.75	0.80	0.85
Then the probability of declaring that the regimen warrants further study is...	0.092	0.233	0.459	0.715	0.904
And the probability of stopping at the interim analysis is...	0.648	0.485	0.314	0.164	0.062

16.33 Other considerations: Adverse events, quality/duration of response, and patterns of treatment failure observed in this study, as well as scientific discoveries or changes in standard care will be taken into account in any decision to terminate the study.

#### 16.4 Analysis Plan

The analysis for this trial will commence at planned time points (see 16.3) and at the time the patients have become evaluable for the primary endpoint. The Statistician and Study Chair will make the decision, in accord with CCS Standard Operating Procedures, availability of data for secondary endpoints (e.g., laboratory correlates), and the level of data maturity. It is anticipated that the earliest date in which the results will be made available via manuscript, abstract, or presentation format is when last patient has been followed for at least 6 months.

**16.41 Primary Outcome Analysis:**

16.411 **Definition:** The primary endpoint of this trial is the confirmed response rate. A success is defined as a sCR, CR, VGPR, or PR noted as the objective status on two consecutive evaluations at any time. All patients meeting the eligibility criteria who have signed a consent form and have begun treatment will be evaluable for response, unless they are determined to be a major violation.

16.412 **Estimation:** The proportion of successes will be estimated by the number of successes divided by the total number of evaluable patients. Ninety-five percent confidence intervals for the true success proportion will be calculated according to the approach of Duffy and Santner.

16.413 **Over Accrual:** If more than the target number of patients are accrued, the additional patients will not be used to evaluate the stopping rule or used in any decision making processes; however, they will be included in final point estimates and confidence intervals

**16.42 Secondary Outcome Analyses**

16.421 **Progression-free survival time** is defined as the time from registration to the time of progression or death due to any cause. A progression that occurs during cycle 1 of the phase II portion prior to the addition of lenalidomide will not be considered an event. Patients who are alive and progression-free will be censored on the date of their last disease assessment. Patients who receive subsequent treatment for myeloma before disease progression will be censored on the date of their last disease assessment prior to initiation of the subsequent treatment. The distribution of progression-free survival will be estimated using the method of Kaplan-Meier.

16.422 **Survival time** is defined as the time from registration to death due to any cause. The distribution of survival time will be estimated using the method of Kaplan-Meier.

16.423 **Duration of response** is defined for all evaluable patients who have achieved a confirmed response as the date at which the patient's objective status is first noted to be a sCR, CR, VGPR, or PR to the earliest date progression is documented. The distribution of duration of response will be estimated using the method of Kaplan-Meier.

16.424 **Adverse Events:** All eligible patients that have initiated treatment will be considered evaluable for assessing adverse event rate(s). The maximum grade for each type of adverse event will be recorded for each patient, and frequency tables will be reviewed to determine patterns. Additionally, the relationship of the adverse event(s) to the study treatment will be taken into consideration.

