#### Phase II

- 2.22 To evaluate the progression free survival (PFS) of the combination of ibrutinib, lenalidomide, and dexamethasone in MM patients
- 2.23 To evaluate the safety profile of this regimen in untreated MM patients.
- 2.24 To evaluate the duration of response for patients treated with this 3-drug regimen.
- 2.25 To evaluate overall survival (OS) for patients treated with this 3-drug regimen

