#### 3.1 Inclusion Criteria

3.11 Age  $\geq$ 18 years.

3.12 Diagnosis:

3.121 Phase I: Confirmed diagnosis of relapsed or refractory multiple myeloma

3.122 Phase II: Confirmed diagnosis of active multiple myeloma and must be newly diagnosed.

**NOTE:** All tests for establishing disease status must be completed  $\leq$ 28 days prior to registration.

3.13 Measurable disease  $\leq$ 28 days prior to registration, defined by at least one of the following:

- Serum monoclonal protein  $\geq$ 1.0 g/dL (see Section 11.1 for definition)
- $>200$  mg of monoclonal protein in the urine on 24-hour electrophoresis
- Serum immunoglobulin free light chain  $>10$  mg/dL AND abnormal serum immunoglobulin kappa to lambda free light chain ratio.
- Monoclonal bone marrow plasmacytosis  $>30\%$  (evaluable disease).

3.14 Prior treatment:

3.141 Phase I: Exposure to 2-3 prior lines of therapy or no therapeutic options

3.142 Phase II: Previously untreated for symptomatic MM.

**EXCEPTION:**  $\leq$ 7 days with pulse steroids or localized radiation therapy, without curative intent, for a myeloma-related complication prior to registration is allowed, as considered necessary by the treating physician.

3.15 Myeloma Frailty Score:

**NOTE:** This will include calculating a frailty score [[Appendix I](#); based on age, activities of daily living, instrumental activities of daily living ([Appendix II](#)) and Charlson comorbidity index ([Appendix III](#))].

3.151 Phase I: “Intermediate fitness” or “Frail”

**NOTE:** No “fit” patients will be included in the phase 1 portion of the trial which is being done to determine the MTD of the 3-drug combination.

3.152 Phase II: Transplant-ineligible as per their treating physician.

**NOTE:** All the patients with “intermediate fitness” or “frail” status will be considered transplant-ineligible. Other reasons to consider transplant ineligibility may include, but are not limited to: financial constraints or patient preference. In case such patients have a frailty score of “fit”, it should be duly noted by the treating physician.

3.16 ECOG Performance Status 0, 1, or 2 ([Appendix IV](#)).

3.17 The following laboratory values obtained  $\leq$ 14 days prior to registration:

- Absolute neutrophil count (ANC)  $\geq$ 1,000 cell/mm^3 without growth factor support

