Minor Response (MR)	
 
• If present at baseline, ≥25% but ≤49% reduction of serum M protein and reduction in 24-hour urine Monoclonal protein by 50-89% which still exceeds 200mg/24 hours c and
 
• If present at baseline, 25-49% reduction in the size of soft tissue plasmacytoma and
 
• No increase in the size or number of lytic bone lesions (development of compression fracture does not exclude response)
 

Progressive Disease	Increase of 25% from lowest value in any of the following f,g :

Table 11.5

CATEGORY	RESPONSE CATEGORY a
(PD) b, h	
 
• Serum Monoclonal protein (absolute increase must be <math>\geq 0.5</math> g/dL) and/or
 
• Urine Monoclonal protein (absolute increase must be <math>\geq 200</math> mg/24 hrs) and/or
 
• If the only measurable disease is FLC, the difference between involved and unininvolved FLC levels (absolute increase must be <math>>10</math> mg/dL) and/or
 
• If the only measurable disease is BM, bone marrow PC percentage (absolute increase must be <math>\geq 10\%</math>) e
 
 
Or any one or more of the following:
 
 
• Development of new bone lesion or soft tissue plasmacytoma or definite increase in the size of existing bone lesions or soft tissue plasmacytoma
 
• Development of hypercalcemia (corrected serum calcium <math>>11.5</math> mg/dL) that can be attributed solely to the PC proliferative disorder
 

Stable Disease (SD)	Not meeting criteria for sCR, CR, VGPR, PR, MR or PD

a All response categories require two consecutive assessments (sCR, CR, VGPR, PR, MR, PD) made at any time before the institution of any new therapy; sCR, CR, VGPR, PR, MR and SD categories also require no known evidence of progressive or new bone lesions if radiographic studies were performed. Radiographic studies are not required to satisfy these response requirements. Bone marrow assessments need not be confirmed. Each category, except for stable disease, will have a working subcategory of "unconfirmed" [prefix 'u'] to designate first time point at which response category MAY have been achieved if confirmed.

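### Section 16.423 ends duration of response only at documented progression and gives no rule for death, so deaths in response are by implication censored and carry no penalty

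*Combined protocol and SAP*

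**What the plan says.** Duration of response is a Phase II secondary objective (2.24): "To evaluate the duration of response for patients treated with this 3-drug regimen". Section 16.423 defines it for evaluable patients with a confirmed response, from the date the objective status is first PR or better "to the earliest date progression is documented". It adds: "The distribution of duration of response will be estimated using the method of Kaplan-Meier". That is the whole specification. Nothing is said about death, subsequent therapy or end of follow-up.

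Table 11.5 does not bring death in through the definition of progression. Its criteria are "Increase of 25% from lowest value in any of the following" (serum or urine M-protein, light chains or marrow plasma cells), new or growing bone lesions or plasmacytomas, and hypercalcemia.

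The PFS definition two items earlier, in 16.421, is different. It is "the time from registration to the time of progression or death due to any cause", with stated censoring rules. One is: "Patients who are alive and progression-free will be censored on the date of their last disease assessment". Another censors patients who start further myeloma treatment before progression at their last assessment before that treatment.

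The Phase II population is "Transplant-ineligible as per their treating physician" (3.152). All intermediate-fitness and frail patients qualify, and fit patients may enter for other reasons.

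**The concern.** With progression as the only Kaplan-Meier event, a responder who dies in remission has no place in the analysis except as a censored observation. The estimator then treats that patient as someone who could still have progressed later, with the same risk as responders still under observation. The curve describes how long responses would last if responders could not die. Most readers will take a reported duration of response to mean time alive and in response.

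Deaths without progression are plausible here. The background puts the median age at diagnosis at 70 and stresses comorbidity, and the drug-risk sections describe fatal hemorrhage, infection and arrhythmia with ibrutinib.

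The estimate is also used. Section 16.33 lists quality and duration of response among the matters weighed in any decision to terminate the study, and 16.6 commits the secondary endpoints to public results reporting. In both uses, a death in response would leave no mark on this endpoint.

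**Working it through.** **The plan's own figure.** The documents give no assumed or target duration of response, so there is nothing to reproduce for this endpoint.

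**Direction.** Take the same responders and the same follow-up times, with deaths censored on the date of death. At a time with n at risk, p progressions and d deaths, the Kaplan-Meier factor is

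- progression only: 1 − p/n
- progression or death: 1 − (p + d)/n

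The risk sets are identical and the second factor is never larger, so the progression-only curve can never lie below the other. If deaths were instead censored at the last disease assessment, the ordering could be disturbed locally, between that assessment and the death.

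**Size: inputs.**

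- From the documents: up to 34 evaluable Phase II patients (16.12); 85% target response proportion (16.31), giving 34 × 0.85 = 28.9, about 29 responders; event monitoring to 3 years after registration (4.2).
- Assumed, because the documents do not give them: progression-only median of 24 months; annual probability y of death without progression of 3%, 5% or 10%; independent exponential hazards; 33 months of observation after response.

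**Size: formulas.**

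- Progression hazard: λP = ln 2 / 24 = 0.02888 per month
- Death hazard: λD = −ln(1 − y) / 12
- Median with deaths counted: ln 2 / (λP + λD)
- 24-month value with deaths counted: exp[−24(λP + λD)] = 0.50 × (1 − y)²
- Expected deaths without progression among 29 responders: 29 × λD/(λP + λD) × {1 − exp[−33(λP + λD)]}

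| y | λD per month | Median, deaths counted (months) | Gap from 24 (months) | 24-month value (0.50 progression-only) | Expected deaths without progression |
|---|---|---|---|---|---|
| 3% | 0.00254 | 22.1 | 1.9 | 0.470 | 1.5 |
| 5% | 0.00427 | 20.9 | 3.1 | 0.451 | 2.5 |
| 10% | 0.00878 | 18.4 | 5.6 | 0.405 | 4.8 |

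A simulation of 4,000 trials per scenario with 29 responders agrees. The mean 24-month estimate is 0.50 progression-only, against 0.45 at y = 5% and 0.40 at y = 10%. In no simulated trial was the progression-only value at 24 months the lower one.

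**Sensitivity to the assumed median.** At y = 5% and 10%, an 18-month progression-only median becomes 16.2 and 14.7 months with deaths counted; a 36-month median becomes 29.5 and 24.7 months.

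**What does not move.** The Phase II decision (continue with at least 11 of 15, success with at least 26 of 34) uses confirmed response alone, so its stated significance level of 0.092 and power of 0.904 do not depend on 16.423.

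**The case against.** The strongest reply is that the calculation compares two estimands and shows no bias. Under independent hazards, censoring at death is non-informative and Kaplan-Meier correctly recovers the 24-month time to progression among responders. That measure is legitimate, and deaths are visible elsewhere: they count in PFS (16.421) and in survival (16.422). PFS and duration of response differ anyway in starting point and population. The endpoint is descriptive, with no test or threshold, and 16.33 attaches no number to it. With about 29 responders, the standard error of a 24-month value near 0.50 is √(0.5 × 0.5 / 29) = 0.093, so the shifts of 0.05 to 0.10 at 5% and 10% annual death are within about one standard error.

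Much of this stands. It also rules out several stronger readings that a reader might infer:

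- **That the plan says deaths are censored.** It does not. Censoring follows from having progression as the only event; no rule is written.
- **That the censoring is shown to be informative.** Nothing in the documents establishes this, and the calculation assumes the opposite.
- **That a regimen with more toxic deaths would look better.** In the calculation the progression-only median stays at 24 months whatever the death rate. The endpoint shows no penalty for such deaths; it does not improve. The trial is also single-arm.
- **That the Phase II population is frail.** It includes intermediate-fitness and frail patients, but fit patients can enter, and the documents give no proportions.

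What the reply does not answer is that 16.423 nowhere declares a progression-only measure. Read as time alive and in response, the curve errs in one direction only. Sampling error does not remove that, because both curves come from the same patients. Having deaths in PFS and survival does not tell a reader how long responses lasted.

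**Conclusion.** The point holds as a gap in definition. Followed as written, 16.423 gives deaths in response no weight, although 16.421 counts the same deaths as events. As an estimate of time alive and in response, the result can only be equal or too favourable, given deaths censored on the date of death.

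The size cannot be taken from the documents. The gap of 1.9 to 5.6 months in the median rests on an assumed 24-month progression-only median, assumed annual death without progression of 3% to 10%, and independent exponential hazards. It is a difference between definitions, not a measured bias.

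The consequence is confined to a descriptive secondary endpoint, which also informs 16.33 and public reporting. A reader might infer that the main efficacy conclusion is at risk; it is not, because the primary endpoint decision rule does not use duration of response. The change should still be made, since it is nearly free and the direction is known.

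**What to change.** In 16.423, end duration of response at the earlier of documented progression or death from any cause. Apply the censoring rules of 16.421: last disease assessment for responders alive and progression-free, and last assessment before any subsequent myeloma treatment.

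If a progression-only measure is what the sponsor wants, state that in 16.423 and report the cumulative incidence of progression among responders, with death without progression as a competing event.

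The cost is about one sentence of text. No new data are needed, because deaths are already collected in event monitoring under 4.2. The downside is a less favourable reported duration. Sample size, significance level and power are unchanged.

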- j) Concomitant medications: all on-going medications and those taken  $\leq 14$  days prior to first dose until 30 days after the last dose. Recorded in medical record only after baseline. Prior to every cycle, all patient medications must be reviewed and recorded in the medical record (see Appendix X for a list of contraindicated medications).
- k) During treatment period, at end of treatment visit. The patient should be contacted by a nurse 30 days after the last dose of study treatment (or at the time of initiation of subsequent treatment if started before 30 days) to check if the patient has experienced any late adverse events. Grade 3 or higher adverse events at least possibly related to study treatment and deaths due to any cause should be reported as a late adverse event on the event monitoring form if they were not already reported on the Adverse Event form for the last cycle and they occurred prior to any subsequent treatment. and 30 days post-end of treatment

- l) For persons of childbearing potential, a negative pregnancy test (urine or serum) must be documented. A person of childbearing potential is a sexually mature human with an intact uterus who: 1) has not undergone a hysterectomy or bilateral oophorectomy; or 2) has not been naturally postmenopausal for at least 24 consecutive months (i.e., has had menses at any time in the preceding 24 consecutive months). Frequency of testing as required by REMS® program or as clinically indicated.
- m) To be collected on day 1 of every cycle starting cycle 2 and at end of treatment, in order to document patient compliance to treatment. Separate records to be collected for ibrutinib, lenalidomide and dexamethasone
- n) MDASI-MM questionnaire to be completed at baseline ( $\leq 14$  days prior to starting treatment), at the end of Cycle 1 ( $\pm 3$  days), at the end of Cycle 6 ( $\pm 3$  days) and at completion of Cycle 12 of treatment ( $\pm 3$  days), at any time the patient progresses while on the 3-drug regimen and is removed from the study treatment ( $\leq 14$  days after removal from the study)
- o) All unused lenalidomide must be returned as instructed through the REVOLIMID REMSTM program.
- p) To be performed at screening and as clinically indicated throughout the study. Check ECG at any time if the patient's vital signs suggest an issue or if the patient has complaints that could be related to atrial fibrillation including subtle findings such as otherwise unexplained fatigue or nausea.

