## 6.3 Phase I and II

## 6.31 Correlative Research:

A mandatory correlative research component is part of this study, the patient will be automatically registered onto this component (see Sections 3.19e and 14.1).

6.32 Prior to accepting the registration, registration/randomization application will verify the following:

- IRB approval at the registering institution

- Patient eligibility
- Existence of a signed consent form
- Existence of a signed authorization for use and disclosure of protected health information

6.33 Documentation of IRB approval must be on file in the Registration Office before an investigator may register any patients.

In addition to submitting initial IRB approval documents, ongoing IRB approval documentation must be on file (no less than annually) at the Registration Office ([contact]). If the necessary documentation is not submitted in advance of attempting patient registration, the registration will not be accepted and the patient may not be enrolled in the protocol until the situation is resolved.

When the study has been permanently closed to patient enrollment, submission of annual IRB approvals to the Registration Office is no longer necessary.

6.34 At the time of registration, the following will be recorded:

- Patient has/had not given permission to store and use his/her sample(s) for future research of multiple myeloma at Mayo.
- Patient has/had not given permission to store and use his/her sample(s) for future research to learn, prevent, or treat other health problems.
- Patient has/had not given permission for MCCC to give his/her sample(s) to researchers at other institutions.

6.35 Treatment on this protocol must commence at Mayo Clinic under the supervision of a medical oncologist/hematologist.

6.36 Treatment cannot begin prior to registration and must begin  $\leq$  28 days after registration.

6.37 Pretreatment tests/procedures (see Section 4.0) must be completed within the guidelines specified on the test schedule.

6.38 All required baseline symptoms (see Section 10.6) must be documented and graded.

6.39a Study drug is available on site.

6.39b Patient questionnaire booklet is available on site; copies are not acceptable for this submission.

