#### 13.6 Ineligibles

A patient is deemed *ineligible* if after registration, it is determined that at the time of registration, the patient did not satisfy each and every eligibility criteria for study entry. The patient may continue treatment off-protocol at the discretion of the physician as long as there are no safety concerns, and the patient was properly registered. The patient will go directly to the event-monitoring phase of the study (or off study, if applicable).

- If the patient received treatment, all data up until the point of confirmation of ineligibility must be submitted. Event monitoring will be required per Section 18.0 of the protocol.
- If the patient never received treatment, on-study material and the End of Active Treatment/Cancel Notification Form must be submitted. No further data submission is necessary.

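### Section 16.424 counts only eligible patients in the adverse event rates, so a patient treated and later found ineligible can drop out of the safety table

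*Combined protocol and SAP*

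**What the plan says.** The safety objective at 2.23 is "To evaluate the safety profile of this regimen in untreated MM patients". The matching analysis is in 16.424: "All eligible patients that have initiated treatment will be considered evaluable for assessing adverse event rate(s". For each patient the worst grade of each event type is recorded, and frequency tables are then examined. To be counted, a patient must be eligible and must have started treatment. Major violations are not excluded here, unlike in the response definition at 16.411.

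Section 16.424 does not name a phase. I read it as phase II for two reasons: it follows the phase II design in 16.3, and phase I has its own adverse event plan in 16.231, which states no eligibility condition.

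Under 13.6, a patient is ineligible if it emerges after registration that any entry criterion was unmet at registration. Some of these patients may already have been treated: "If the patient received treatment, all data up until the point of confirmation of ineligibility must be submitted". The same section adds: "The patient may continue treatment off-protocol at the discretion of the physician as long as there are no safety concerns". The patient then goes to event monitoring, or off study where that applies.

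Footnote k of the test schedule in 4.1 covers late events. "The patient should be contacted by a nurse 30 days after the last dose of study treatment", and "Grade 3 or higher adverse events at least possibly related to study treatment and deaths due to any cause should be reported" as late events if they were not already reported and "they occurred prior to any subsequent treatment".

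**The concern.** An eligibility condition makes sense for response, where the question is activity in the intended population. A safety rate describes what happened to people who took the drugs, and a patient found ineligible after starting treatment did take them. Several entry criteria are themselves safety screens, such as creatinine clearance, platelets, PT/INR, bleeding history, cardiac illness and hepatic impairment. A patient who failed one of these and was treated is informative about toxicity.

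Read together, 16.424 and 13.6 allow a patient to be treated, have a toxicity and have it submitted, yet be absent from the table that answers objective 2.23. This matters most for a rare event type in a group of about 34, where one patient separates zero from non-zero.

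**Working it through.** **Is there a route back into the rates?**

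- 16.424: eligible and treated.
- 13.6: treated ineligible patients are foreseen, and their data are required up to confirmation of ineligibility.
- 10.6: routine reporting of grade 3 and 4 events regardless of attribution, with no eligibility condition. This governs what is submitted, not who is in the rate.
- 16.52, phase II: the stopping rule counts treated patients among the first 15, and all patients after that.
- 16.33: adverse events observed in the study inform any decision to terminate, with no eligibility condition.

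None of these adds treated ineligible patients to the 16.424 rates.

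**How many could be affected?** Section 16.12 gives at most 24 evaluable patients in phase I and 34 in phase II, plus 5 extra (2 and 3). The stated total reproduces: 24 + 34 + 5 = 63, and phase II alone is 34 + 3 = 37. The 3 extra phase II places cover ineligibility, cancellation, major violation and other reasons together. Cancelled patients were never treated (13.8). The number treated and then found ineligible, k, is therefore not stated and may be 0. I assume k = 0 to 3.

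**Effect on a common rate.** Assume 34 eligible treated patients, 5 of them with the event. The plan would report 5/34 = 14.7%. The exact (Clopper-Pearson) 95% interval is 5.0% to 31.1%, used here only as a yardstick, since 16.424 specifies no interval. The all-treated rate lies between 5/(34 + k), if no ineligible patient had the event, and (5 + k)/(34 + k), if all did.

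| k | Share left out | None had the event | All had the event | Shift from 14.7% (points) |
|---|---|---|---|---|
| 0 | 0% | 5/34 = 14.7% | not applicable | 0 |
| 1 | 1/35 = 2.9% | 5/35 = 14.3% | 6/35 = 17.1% | −0.4 to +2.4 |
| 2 | 2/36 = 5.6% | 5/36 = 13.9% | 7/36 = 19.4% | −0.8 to +4.7 |
| 3 | 3/37 = 8.1% | 5/37 = 13.5% | 8/37 = 21.6% | −1.2 to +6.9 |

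Every point estimate lies inside 5.0% to 31.1%. The top value needs all three extra places to be treated ineligible patients, and all three to have the event.

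**Effect on a rare event.** Suppose an event type occurs only in one treated ineligible patient and k = 1. The plan reports 0/34, with exact upper limit 1 − 0.025^(1/34) = 10.3%. Counting everyone treated gives 1/35 = 2.9% (exact 95% interval 0.1% to 14.9%). The estimates are statistically compatible, but the table shows zero for an event that occurred.

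**The case against.** The strongest reply is that this is an openly stated choice of analysis set, not a contradiction. The eligibility condition matches the one for response in 16.411. Objective 2.23 concerns untreated patients, so someone found ineligible because of earlier therapy lies outside it. Eligibility is also checked at entry: "Prior to accepting the registration, registration/randomization application will verify the following", and the list that follows includes eligibility. The effect is hypothetical, and 16.424 does not bar a separate listing of events in other patients.

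Much of this stands. The plan does not contradict itself, the entry check makes such patients less likely, and the effect on common rates is probably small. But 13.6 still provides for these patients, and wishing to describe the target population is no good reason to leave exposed patients out of the main safety denominator. A supplementary eligible-only table would serve that wish.

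A reader might infer more than the documents support:

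- *That toxicity in these patients goes unmonitored.* It does not. Serious event, death and routine reporting state no eligibility condition, the monitoring board reviews safety at least twice a year (16.51), and 16.52 and 16.33 are not limited to eligible patients.
- *That the different denominators in 16.424 and 16.52 prove an error.* They do not. The wording of 16.52 is naturally read as the wider set but does not mention ineligible patients. It supports consistency and nothing more.
- *That the reported rates will be too low.* The direction is not fixed. Some criteria bear on toxicity risk and others need not, and ineligible patients may be observed for less time.
- *That the plan expects three such patients.* The three places cover every reason for loss, including patients never treated.

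**Conclusion.** The concern holds as a minor one, and the change is a cheap improvement. Followed literally, 16.424 leaves treated patients who are later found ineligible out of the adverse event rates for objective 2.23. The textual reading is firm, apart from the phase II label, which is inferred from placement. A material effect is not shown. The size rests on assumed values, k between 0 and 3 and 5 events in 34. On those values the rate moves by −1.2 to +6.9 points and stays within the interval already implied by 5/34. The clearer harm is an event type shown as 0/34 when one treated patient had it. No decision rule uses the 16.424 tables.

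**What to change.** Replace the first sentence of 16.424 with one to this effect: every patient who started study treatment, whether or not later found ineligible, counts in the adverse event rates. Name the phase to which the section applies. Use the data already submitted under 13.6, together with any later events that existing reporting captures, including footnote k of 4.1. State the number of treated ineligible patients and that their observation may be shorter. An eligible-only table may be kept as a supplement.

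A special observation window for these patients is not needed. Cutting off events once treatment continues off-protocol could itself omit a related event arising just after ineligibility is confirmed.

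The cost is a short text change. Data are assured only up to confirmation of ineligibility. Later capture is not guaranteed, because 13.6 allows a patient to go off study, and the report should say so. The small downside is that a few patients outside the target population, with shorter observation, enter the rates and may dilute them slightly. The response-evaluable set, the 16.52 stopping rule, sample size, alpha and power do not change.
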